8 STUDY ASSESSMENTS AND PROCEDURES

The Electronic Data Capture (EDC) system will be used for data collection and query handling. The Investigator will ensure that data are recorded on the electronic Case Report Forms (eCRF) as specified in the study protocol and in accordance with the instructions provided.

Except for the questionnaires to be completed by participants (see SOA), all data will be based on what have been generated during routine clinical practice. Data collection for all enrolled patients will follow up version 2.0.

Baseline data collection

At baseline visit (V0, week -12), the following patient data will be collected from patients:

- Demographic information

- Vital signs include body mass index
- Subject Status
- Asthma history, comorbidities, and medications (historical data)
- Laboratory and clinical testing within 3 months (if available in medical records), including CBC with differentiation, blood gas analysis (pH, SaO₂, PaO₂, PaCO₂, and HCO³⁻), C-reactive protein, skin allergen prick, total IgE or specific IgE, PFT (pulmonary function testing), BPT (bronchial provocation test), PEF (peak expiratory flow) and FeNO (fractional exhaled nitric oxide)
- Current visit asthma treatment information
- Two patient-reported outcomes (PRO) questionnaires (ACQ-5 and AQLQ(S)+12)
- MARS-A questionnaire
- Questionnaire of asthma knowledge for patient
- Inhale skill score for patient
- Patient's expectation for asthma treatment

Follow up data collection

After the initiation of the intervention program, participants will return to the study hospital every 12 weeks for on-site follow-up visits (V1 to V5), in accordance with guideline recommendation. During on-site visits, the usual care activities can be performed as needed.

Participants are encouraged to come back to the study hospital if they have asthma-related conditions or symptoms worsening. If in emergency case, they can choose to visit a hospital other than the study hospital, and they should report it to study pulmonologists or study staffs once it is possible. In case there are data generated from other hospitals that need to be collected as per protocol, i.e. hospitalization due to exacerbation, the data and supportive documents (e.g., medical record of hospitalization summary) will be required at next on-site visit.

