9.4.2 Effectiveness

9.4.2.1 Primary Endpoint(s)

Change from baseline in the proportion of patients with an ICS-based maintenance and/or reliever treatment at week 48

Prescription will be used to define this endpoint. The primary analysis will use mixed effect logistic regression model, taking the measurement timepoint (baseline/post-baseline) as the fixed effect, hospital, pulmonologist and patient as the random effects. In case of lack of convergency, hospital and pulmonologist factors will be removed from the model. Within the framework of this model, the 95% confidence interval and p value of the primary endpoint will be estimated and presented. The analysis will be performed in FAS.

Another sensitivity analysis will be conducted with generalized estimating equations (GEE) model using the same covariates as the primary analysis.

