3.1.2 Baseline Definition

Unless otherwise stated, general baseline will be defined as the last non-missing evaluation on or prior to Visit 0. Baseline definitions of comorbidities and treatments are provided in the comorbidities, medications and prescriptions sections (refer to section 4.1.8 and 4.1.9).

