4.1.9 Prescriptions

Prescribed medication for asthma will be coded using the World Health Organization Drug Dictionary (WHO DD) of the version currently in effect at the time of database lock. The number and percentage of patients who are prescribed for asthma will be summarized respectively by ATC medication class 2 and WHO DD preferred term (PT) and visit in the FAS. Prescriptions will also be presented in a listing.

If treatment is prescribed at least once within 3months before Visit 0 (week -12), the subjects will be regarded as receiving this treatment at baseline. For Visit 2 (week 12), if treatment is prescribed at least once on or after Visit 1 and on or before Visit 2, the subjects will be regarded as receiving treatment at this visit. For Visit 3 -Visit 5 (week 24, 36 and 48), if treatment is prescribed at least once after last visit and on or before this visit, the subjects will be regarded as receiving treatment at this visit.

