4.2.1 Primary Endpoint

4.2.1.1 Definition

The primary endpoint is the proportion of patients with an ICS-based maintenance and/or reliever treatment, which is indicated by whether or not the treatment option includes ICS-containing medication. Change from baseline in the proportion of patients with an ICS-based maintenance and/or reliever treatment at week 48 will be analysed.

Doctor's prescription will be used to define this endpoint. The baseline and following analysis visits' definitions refer to section 4.1.9.

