4.2.1.2 Primary Analysis of Primary Endpoint

Proportion of patients with an ICS-based maintenance and/or reliever treatment will be described using the frequency with ICS and corresponding percentage at baseline and week 48.

The primary analysis will use mixed effect logistic regression model, taking the measurement timepoint (baseline/post-baseline) as the fixed effect, hospital, pulmonologist and patient as the random effects. Logit link function will be used, and the model parameters will be estimated by maximum likelihood approach. The compound-symmetry variance-covariance structure will be used. In case of lack of convergency, hospital and prescriber factors will be removed from the model.

Within the framework of this model, first predict for all patients the probability of ICS usage at baseline/ post-baseline and then take the average over baseline/ post-baseline patients to get an estimate of proportion, and finally take the difference between the two proportions as the risk difference estimate, the 95% confidence interval of risk difference in proportion by bootstrapping method will be estimated and presented. Besides, Odds Ratio and P value from the model will also be estimated and presented. The analysis will be performed in FAS. Reference SAS code is shown in section 7.

If medication is taken at least once within 3 months before Visit 0 (week -12), the patients will be regarded as taking this medication at baseline. For Visit 2 (week 12), if medication is taken at least once on or after Visit 1 and on or before Visit 2 (within 3 months before this visit), the subjects will be regarded as taking medications at this visit. For Visit 3 -Visit 5 (week 24, 36 and 48), if medication is taken at least once after last visit and on or before this visit (within 3 months before this visit), the subjects will be regarded as taking medication at this visit.

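### SAP 4.1.9 counts ICS prescriptions differently at baseline and week 48 (visit day and uncapped look-back), and 4.2.1.2 adds an unlabelled rule on medication taken

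*SAP*

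**What the plan says.** Both documents base the primary endpoint on prescriptions: "Prescription will be used to define this endpoint" (protocol 9.4.2.1) and "prescription will be used to define this endpoint" (SAP 4.2.1.1). SAP 4.2.1.1 sends the definitions of baseline and later visits to SAP 4.1.9, which has three rules:

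- Baseline: "If treatment is prescribed at least once within 3months before Visit 0 (week -12").
- Week 12: "if treatment is prescribed at least once on or after Visit 1 and on or before Visit 2".
- Weeks 24, 36 and 48: "if treatment is prescribed at least once after last visit and on or before this visit".

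The general baseline rule in SAP 3.1.2 does include the Visit 0 day ("general baseline will be defined as the last non-missing evaluation on or prior to Visit 0"), but that section refers treatments to 4.1.8 and 4.1.9. Protocol section 8 lists "Current visit asthma treatment information" among the data collected at Visit 0.

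The last paragraph of SAP 4.2.1.2, inside the primary analysis section, gives a parallel set of rules for medication taken. For weeks 24 to 48 it reads "if medication is taken at least once after last visit and on or before this visit (within 3 months before this visit"). It carries no label and no reference to 4.1.9. SAP 4.2.1.3 plans only a GEE sensitivity analysis, and 4.2.1.4 (supplementary analyses) is marked not applicable.

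**The concern.** The study is a single-arm before/after comparison. With a concurrent control, a difference in how ICS use is counted at two time points would largely cancel. Here it goes straight into the primary estimate, for which the study is powered at a 5-point change.

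Two features of 4.1.9 differ between baseline and week 48. The first is the visit day, which counts at week 48 but, on a literal reading, not at baseline. Because the week 12 rule starts at Visit 1, an ICS prescription written on the Visit 0 day would then count at no time point. Visit 0 precedes the training, and protocol 4.1 admits newly seen patients, so such prescriptions are both legitimate baseline data and plausible.

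The second is the length of the look-back, which is fixed at baseline and open-ended at week 48. The SAP does not say what the last visit is for a patient who missed week 36.

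The paragraph on medication taken is a separate problem. It uses a different event and a different limit from the governing definition, within the section that a programmer will follow for the primary analysis.

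**Working it through.** **1. Yardstick.** Inputs from SAP 1.3: 40% to 45%, correlation 0.25, 30% missing at week 48, 80% power, alpha 0.05 (two-sided, from protocol 9.1). Using all baseline data and 70% of week-48 data:

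n = (1.960 + 0.842)² × [0.24 + 0.2475/0.7 − 2 × 0.25 × √(0.24 × 0.2475)] / 0.05² = 1481.

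This agrees with the planned 1500 or so. The sample size is not in dispute; the 5 points serve only as a scale.

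**2. The rules side by side.**

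| | Baseline, 4.1.9 | Week 48, 4.1.9 | Week 48, last paragraph of 4.2.1.2 |
|---|---|---|---|
| Event | prescribed | prescribed | taken |
| Visit day | not stated as included | included | included |
| Start of look-back | 3 months earlier | after last visit | after last visit |
| Cap | 3 months | none | 3 months |

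**3. Length of look-back.** Visit tolerances are ±7 days at weeks 24, 36 and 48 (protocol 1.3).

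- Baseline: 3 calendar months, 89 to 92 days.
- Week 48, week 36 attended: 84 ± 14 = 70 to 98 days.
- Week 48, week 36 missed, last visit read as last attended: 168 ± 14 = 154 to 182 days.
- The analysis windows in SAP 3.1.4 allow more. With week 36 attended: 295 − 294 = 1 to 378 − 211 = 167 days. With week 36 missed: 295 − 210 = 85 to 378 − 127 = 251 days.

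**4. Direction.** Leaving out Visit 0-day prescriptions can only hold or lower baseline, so it can only hold or raise the change. A longer look-back after a missed visit can only hold or raise week-48 use. The on-schedule difference (84 days against about 91) works the other way.

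**5. Scale of the look-back effect (illustration only).** Assume no true change and 40% prescribed ICS in 91 days.

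- Model A, same constant rate for everyone: P(L) = 1 − 0.60^(L/91). P(84) = 37.6% (−2.4 points); P(168) = 61.1% (+21.1).
- Model B, rates vary between patients (gamma): P(L) = 1 − (1 + θL/91)^(−k). Setting P(91) = 0.40 and a correlation of 0.25 between two separate 91-day windows gives θ = 0.534, k = 1.195. P(84) = 38.0% (−2.0); P(168) = 55.9% (+15.9).

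If a share s of week-48 patients missed week 36, the net shift is (1 − s) × shift at 84 days + s × shift at 168 days:

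| s (assumed) | Model A | Model B |
|---|---|---|
| 0% | −2.4 | −2.0 |
| 10% | −0.1 | −0.2 |
| 20% | +2.3 | +1.6 |
| 30% | +4.6 | +3.4 |

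If the same patients are always prescribed ICS, the shift is 0.

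**6. Visit 0 day (literal reading).** If a share q of patients have their only qualifying ICS prescription on that day, baseline falls by q and the change rises by q. The documents give no value for q.

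**The case against.** The case for leaving the plan alone has several parts.

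*Prescription clearly governs.* This stands. A reader might infer that the SAP has two competing primary endpoints, but SAP 4.2.1.1 and protocol 9.4.2.1 agree, so the paragraph in 4.2.1.2 is misplaced text and not a rival definition. The SAP amendment history adds that the prior and concomitant medication page does not collect the investigator's ID. If the data on medication taken come from that page (an inference), that page alone could not supply the pulmonologist effect in the model. The exploratory sections are blacked out, so it cannot be said that the paragraph has no use anywhere, only that it has no stated role where it sits.

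*Three months and 12 weeks are used interchangeably.* This largely stands. Protocol 4.2 justifies 12-week visits by a 3-month recommendation, and protocol 6.7 calls the recruitment period 3 months although Visit 0 is at week −12. The on-schedule difference in length is not the point.

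*Omitting the Visit 0 day may be unintended.* Possibly so. Protocol section 8 collects current treatment at Visit 0, and SAP section 2 declares no departure from the protocol. Protocol 6.7 also discloses that changes during the 3 months before the intervention are not captured. But that statement does not settle the Visit 0 day itself, and 4.1.9 writes the visit day in for follow-up and not for baseline.

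*The bias figures rest on assumptions.* This stands. A constant rate ignores that prescribing clusters at visits, and a missed week 36 also removes an occasion to prescribe. Nothing in the documents supports 30% of week-48 patients having missed week 36; the only 30% given is for missing at week 48.

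**Conclusion.** The point holds as a mismatch in a stated rule, not as a demonstrated bias. SAP 4.1.9 counts the visit-day prescription at week 48 but not, as written, at baseline, and it lets the week-48 look-back reach 154 to 182 days by schedule after a missed week 36, against 3 months at baseline. Both features can only hold or raise the apparent improvement in a study without a control arm. The second depends on reading the last visit as the last attended one; if the scheduled week-36 time point is meant, only the on-schedule difference remains.

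The size cannot be derived from the documents. Under the assumptions shown, the net look-back effect runs from −2.4 to +4.6 points, or −2.0 to +3.4 with the SAP's correlation of 0.25, and it is zero under fully persistent prescribing.

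A reader might infer that the Visit 0 omission alone could produce the 5-point change for which the study is powered. That does not follow: the share of patients affected is unknown, and choosing a share of 5% to obtain 5 points is circular.

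**What to change.** In SAP 4.1.9:

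- (a) Define baseline as at least one prescription on Visit 0 or within the 3 months before it, so that the visit day is treated as at week 48.
- (b) Add to the follow-up rule the 3-month cap already written in 4.2.1.2, and define the last visit as the last attended visit. A missed visit then cannot stretch the look-back beyond the baseline length.

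In SAP 4.2.1.2:

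- (c) Delete the paragraph on medication taken, or move it to 4.2.1.4 as a labelled supplementary analysis.

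In SAP 4.2.1.3:

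- (d) Report the present literal rule of 4.1.9 as a sensitivity analysis.

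Under the illustration above, the cap removes the upward part. Patients who missed week 36 shift by 0, and the rest keep the small on-schedule shortfall. The net is then (1 − s) × (−2.4), which is −2.4 at s = 0 and −1.7 at s = 30%.

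A single 84-day window at every visit is less attractive, because it picks up the previous visit's prescription whenever the gap is 83 days or less.

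The cost is SAP wording and one extra derivation, using prescription and visit dates that 4.1.9 already needs. The observed change may come out slightly smaller once Visit 0-day prescriptions count at baseline. Secondary endpoint 2 also refers to 4.1.9 (SAP 4.2.2.2), so it is corrected by the same edit.

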4.2.1.3 Sensitivity Analyses of the Primary Endpoint

Sensitivity analysis will be conducted with generalized estimating equations (GEE) model using measurement timepoint (baseline/post-baseline) as the fixed effect, and subject ID is used to identify individual subjects. Reference SAS code is shown in section 7. Logit link function will be used for binary distribution. The model parameters are estimated by generalized estimating equations. Compound-symmetry working correlation matrix will be used to model the correlation of the responses from subjects.

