9 STATISTICAL CONSIDERATIONS

9.1 Statistical Hypotheses

The change in GINA guideline-recommended treatment after guideline education and implementation, will be compared between the proportion of patients on with an ICS-based maintenance and/or reliever treatment at Week 48 and the proportion at baseline. For each treatment arm, the proportions along with the 95% confidence intervals the rates and the difference Δ will be computed. The hypothesis test is formed as follows:

The null hypothesis to be tested is:

H_0 : Proportion of patients with ICS-based maintenance and/or reliever treatment at baseline =
Proportion of patients with ICS-based maintenance and/or reliever treatment at Week 48

Against the alternative hypothesis:

H_a : Proportion of patients with ICS-based maintenance and/or reliever treatment at baseline \neq
Proportion of patients with ICS-based maintenance and/or reliever treatment at Week 48

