9.2 Sample Size Determination

Approximately 1500 participants will provide 80% power at a significant level of 0.05 to detect a change from baseline in the proportion of patients with an ICS-based maintenance and/or reliever treatment at week 48 of 5% (Zhao et al 2014). The baseline proportion is assumed to be 40% and a within-participants correlation is assumed to be 0.25. The proportion of missing postbaseline assessment at week 48 is assumed to be 30%.

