1.3 Number of Subjects

Approximately 1500 participants will provide 80% power at a significant level of 0.05 to detect a change from baseline in the proportion of patients with an ICS-based maintenance and/or reliever treatment at week 48 of 5%. The baseline proportion is assumed to be 40% and a within-participants correlation is assumed to be 0.25. The proportion of missing postbaseline assessment at week 48 is assumed to be 30%.

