3.1.7 Handling of Missing Data

Missing data will not be imputed unless otherwise specified elsewhere in the SAP.

Missing dates or partially missing dates will be imputed conservatively for adverse events and prior or concomitant medications/procedures.

For comorbidities, medications and prescriptions sections, incomplete (i.e., partial missing) date will be imputed.

Incomplete End Date:

If missing day and month, then December 31 will be assigned to the missing field.

If missing day only, then the last day of month will be assigned to the missing field.

If the death date is complete and the imputed end date is after the death date, then the end date will be imputed using the death date.

Incomplete Start Date/Baseline Prescribed Date

If missing day and month, then January 1 will be assigned to the missing field.

If missing day only, then the first day of month will be assigned to the missing field.

If the imputed start date is after the end date, then the start date will be imputed using the end date.

If the imputed baseline prescribed date is after the planned start date, then the baseline prescribed date will be imputed using the planned start date.

Otherwise, do not impute.

For incomplete asthma symptoms start date or asthma diagnosed date, the imputation will follow as below:

If missing day and month, then January 1 will be assigned to the missing field.

If missing day only, then the first day of month will be assigned to the missing field.

Otherwise, do not impute.

By-visit endpoints will be analyzed using observed data, unless otherwise specified. For observed data analyses, missing data will not be imputed and only the observed records will be included.

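### No planned analysis varies the missing-data assumption for the primary endpoint, although 30% of week-48 assessments are expected to be missing

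*SAP*

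**What the plan says.** Protocol 9.2 plans for substantial loss: "The proportion of missing postbaseline assessment at week 48 is assumed to be 30" per cent. SAP 1.3 repeats the figure.

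SAP 3.1.7 sets the handling rule: "Missing data will not be imputed unless otherwise specified elsewhere in the SAP". For by-visit endpoints it adds that "missing data will not be imputed and only the observed records will be included".

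SAP 4.1.2 limits the full analysis set (FAS) to enrolled patients with at least one post-intervention treatment assessment. SAP 4.2.1.2 fits the primary mixed logistic model by maximum likelihood in that set.

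SAP 4.2.1.3 then gives a single check: "Sensitivity analysis will be conducted with generalized estimating equations (GEE) model using measurement timepoint (baseline/post-baseline) as the fixed effect", with a compound-symmetry working correlation. The sample code in SAP 7.2 has no weights and no dropout model. SAP 4.2.1.4, on supplementary analyses of the primary endpoint, is marked not applicable.

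The only other item on missingness is the set of subgroups by completion status at weeks 24 and 48 (Protocol 9.4.3, SAP 4.2.4). Both documents class these as exploratory.

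**The concern.** A sensitivity analysis for missing data should ask what happens if the patients who are not seen differ from those who are. The planned GEE does not ask this. It reads the same observed records as the mixed model, and both methods estimate the week-48 proportion from patients who have data. If dropout depends on the unobserved week-48 ICS status, both can be wrong by similar amounts and still agree.

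The single-arm pre/post design makes this matter. There is no concurrent group in which the same dropout would occur, so any difference between retained and lost patients goes directly into the estimated change. About 450 of 1500 patients (30%) would have no week-48 value, and the effect the study is powered for is only 5 points.

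The completion-status subgroups show who is missing and how those patients looked earlier. They cannot supply the absent week-48 outcomes or vary the assumption about them.

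**Working it through.** **Inputs.** From SAP 1.3: "Approximately 1500 participants will provide 80% power at a significant level of 0.05 to detect a change from baseline", with a 5-point change, and "The baseline proportion is assumed to be 40% and a within-participants correlation is assumed to be 0.25". Missing at week 48 is d = 0.30. The test is taken as two-sided because Protocol 9.1 writes the alternative as an inequality. My assumption is that the observed 70% are at 45% at week 48, which is the design effect.

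**1. Reproduce the sample size.** With p1 = 0.40, p2 = 0.45, v1 = 0.24, v2 = 0.2475 and ρ = 0.25, using all baselines and the observed week-48 values on the logit scale:

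- n = (1.960 + 0.842)² × [1/v1 + 1/((1−d)v2) − 2ρ/√(v1v2)] / (logit p2 − logit p1)²
- = 7.849 × [4.167 + 5.772 − 2.052] / 0.2048² ≈ 1,477

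Power at 1500 is 80.6%. The risk-difference version gives 1,481. A paired complete-case calculation inflated for 30% loss gives 1,640 and does not reproduce 1500. So the stated figure fits a calculation in which missingness only costs precision.

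**2. Vary the rate among the missing.** Let m be their week-48 ICS rate. The overall change is 0.7 × 45% + 0.3 × m − 40%.

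| m | Change (points) |
|---|---|
| 45% | +5.0 |
| 40% | +3.5 |
| 35% | +2.0 |
| 30% | +0.5 |
| 28.3% | 0.0 |
| 25% | −1.0 |

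The extremes (m = 0 and m = 100%) are −8.5 and +21.5.

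**3. Where the confidence limit reaches zero.** The planned available-data variance is v1 + v2/0.7 − 2ρ√(v1v2) = 0.24 + 0.3536 − 0.1219 = 0.4717, so SE = √(0.4717/1500) = 1.77 points. The lower 95% limit is zero when the change is 1.96 × 1.77 ≈ 3.48 points. That gives m = (0.40 + 0.0348 − 0.315)/0.3 ≈ 39.9%, about 5 points below the observed rate. This is an approximation that keeps the planned SE and ignores clustering.

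**4. The missing keep their own baseline status.** Their within-patient change is exactly zero, so the SE in step 3 does not apply.

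- Variance of the change among the observed: 0.24 + 0.2475 − 0.1219 = 0.3656.
- Overall variance: 0.7 × (0.3656 + 0.05²) − 0.035² = 0.2565.
- SE = √(0.2565/1500) = 0.0131, and z = 0.035/0.0131 ≈ 2.68.

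The 1,050 complete pairs alone give 0.05/√(0.3656/1050) ≈ 2.68. This scenario reduces the estimate but leaves significance where it was.

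**5. Would the GEE reveal a problem?** The true change is +5.0 with 30% missing in every scenario. The dropout patterns are my assumptions.

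- *Dropout depends on baseline ICS; baseline and week 48 only.* The GEE gives +4.84 (retention 85% on ICS, 60% off) or +4.62 (92.5% and 55%). A saturated random-intercept likelihood model recovers +5.0.
- *Dropout depends on ICS at the previous visit, odds ratio 2 to 4; simulation of 400,000 patients and five visits.* With all visits, the GEE gives +5.04 to +5.05 and the mixed model +5.04 to +5.07. With baseline and week 48 only, both give about +6.1 to +6.9.
- *Dropout depends on week-48 ICS itself, retention 80% on and 61.8% off.* The observed week-48 rate is 0.36/(0.36 + 0.3399) = 51.4%, an apparent change of +11.4. Neither planned model is designed to correct this.

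In the simulation the two models stay close to each other whether they are right or wrong.

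**6. Range.** The zero-change rate among the missing is 20% if 20% are missing and about 12% if 15% are missing. It cannot be reached if 10% are missing. At 30% missing it also cannot be reached once the observed rate exceeds 0.40/0.7 ≈ 57%.

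**The case against.** Five points can be made for the plan.

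**The GEE's assumption does little harm.** Unweighted GEE generally needs a stricter missingness assumption than a likelihood model, and a reader might infer that this makes the check badly biased. The calculations do not support that. Under baseline-dependent dropout the GEE is off by less than 0.4 points, towards a smaller effect. With all visits both models are almost unbiased. This stands, so the gap is the absence of any analysis that lets the missing differ from the observed.

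**The size and direction of selection are not in the documents.** If the missing also began at 40%, a zero change needs them to fall 11.7 points while the observed rise 5. Protocol 2.1 cites reluctance to use ICS as a reason for poor adherence, which makes selective loss conceivable. No passage says that patients lost to follow-up hold fewer ICS prescriptions. This stands, and the figures above are illustrations only.

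**Retaining treated patients need not inflate the result.** If retention follows earlier observed ICS status and all visits enter the model, the distortion is under 0.1 point. This stands, but it depends on which visits enter. SAP 4.2.1.2 describes the timepoint as baseline/post-baseline, while the code in SAP 7.1 models visit and names no estimation method. The primary model's validity under missing at random is therefore not settled by the text.

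**Missingness is described and mitigated.** The completion-status subgroups cover the primary endpoint. The protocol also provides modified follow-up options and a discontinuation visit (7.2), repeated contact (7.3), records from other hospitals (6.7) and telephone follow-up (11.9). The endpoint rests on prescriptions, so a missed visit need not mean an unknown status. These measures may bring missingness below 30%. They do not test the assumption about whatever remains missing.

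**Other biases may be larger.** Protocol 6.7 itself names the lack of a concurrent comparator and the Hawthorne effect.

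**Conclusion.** The point holds as a gap in the sensitivity analysis. With 30% missing expected, no imputation, an FAS that removes patients with no post-intervention assessment, and one unweighted GEE on the same records, nothing planned varies the missingness assumption. Dropout related to unobserved week-48 ICS status is the main missing-data threat to the primary result, alongside the single-arm biases the protocol already admits. The documents do not support calling it the main threat to the study as a whole.

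On size, the 5-point gain falls to 3.5 points if the missing are at 40% and disappears if they are at 28.3%. With the planned SE, the lower 95% limit reaches zero at about 40%. These figures assume 45% among the observed, exactly 30% missing, and no clustering.

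A reader might infer that significance is lost as soon as missing patients simply stay as they were at baseline. That is not so. When each keeps his or her own baseline status, z is about 2.7. The result becomes fragile only if their rate is set at 40% with the wider available-data SE retained, or if their rate is lower still.

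**What to change.** Add to SAP 4.2.1.3 a delta-adjusted multiple-imputation tipping-point analysis in all enrolled patients:

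- Impute week-48 ICS status from baseline status, last observed status and hospital.
- Lower the odds of ICS among the missing in steps until the conclusion changes, and report the estimate and 95% interval at each step.
- Include a row in which the missing keep their baseline status.
- Set the grid in advance. On the figures above, a zero change corresponds to a marginal odds ratio, missing to observed, of (0.283/0.717)/(0.45/0.55) ≈ 0.48. The grid should extend below that.

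State in SAP 4.2.1.2 that all post-baseline visits enter the primary likelihood model, and bring the code in SAP 7.1 into line. If the GEE is kept, weight it by the inverse probability of being observed.

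The cost is one SAP paragraph and one table, with no new data collection. The downside is that the result may look less favourable. If missingness proves low or observed ICS use high, the same table will strengthen the conclusion.
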